2.2 Secondary Objectives

2.2.1. To determine if hypofractionated conformal proton beam treatment will result in local progression (5-year rate in PROG was 7%), disease-specific survival, freedom from biochemical failure (3-Year Actuarial rate in PROG was 96% for low risk patients, 90% for intermediate/high risk patients), and overall survival (5 year OS in PROG was 97%) that are no worse than those achieved with our current institutional standard.

2.2.2. To determine the incidence of acute and late GI and GU morbidity treated with hypofractionated conformal proton beam treatment.

3.0 Patient Selection

3.1. Criteria for eligibility

- 3.1.1. Histologically confirmed adenocarcinoma within 180 days of registration.
- 3.1.2. History and Physical Examination, including digital rectal exam, within eight weeks prior to registration
- 3.1.3. Histologic evaluation of prostate biopsies at LLUMC with assignment of Gleason's Score to the specimen
- 3.1.4. Clinical stage T1-T2C as per the AJCC, 6th edition, and Gleason Score 2-6, and PSA < 10 ng/ml within 180 days prior to registration
- 3.1.5. KPS ≥ 90
- 3.1.6. Age > 18
- 3.1.7 Patient must sign study-specific informed consent

3.2 Conditions for Ineligibility

- 3.2.1. Prior or concurrent invasive malignancy (excluding non-melanomatous skin cancer) or lymphomatous or hematologic malignancies unless continuously disease-free for a minimum of five years
- 3.2.2. Evidence of distant metastasis
- 3.2.3. Regional lymph node involvement
- 3.2.4. Previous radical surgery (radical prostatectomy) or cryosurgery for prostate cancer
- 3.2.5. Previous pelvic irradiation, prostate brachytherapy, or bilateral orchectomy
- 3.2.6. Previous hormonal therapy
- 3.2.7. Previous or concurrent cytotoxic chemotherapy for prostate cancer
- 3.2.8. History of Ulcerative Colitis or Crohn's Disease
- 3.2.9. Concurrent Coumadin administration
- 3.2.10. AIDS

4.0 Pretreatment Evaluation

- 4.1. History and Physical Examination, including digital rectal examination.
- 4.1.1. Completion of baseline urinary status questionnaire.
- 4.1.2. Evaluation of pelvic lymph node status by non-contrast CT 3-D planning scan.
- 4.1.3. MRI/MRS. Endo-rectal MRI/MRS is optional and recommended in patients who are clinically stage T2B-T2C. MRI evidence of upstaging to T3a-T3b will not be taken into account for eligibility determinations unless these findings are collaborated pathologically however, MRI/MRS data on staging will be used to analyze impact of MRI upstaging on biochemical freedom from relapse, disease-specific survival, and overall survival.
- 4.1.4. Pre-treatment PSA as per Section 3.1.5.
- 4.1.5. Histologic review of biopsy specimens as per Section 3.1.3.

5.0 Registration

5.1 Patient registration as per LLUMC institutional standards for participation in clinical trials.

6.0 Radiation Therapy

6.1. All treatment will be delivered with conformal proton beams. Minimum beam energy will be 225 MeV.

6.1.1. All fields will be treated daily.

6.2 Immobilization, and CT Scanning

6.2.3. All patients will be immobilized in a full body immobilization device, while positioned supine. A water balloon will be placed into the rectum at the time of immobilization as per our institutional standard.

6.2.4. Following immobilization a treatment planning CT will be performed as per our institutional protocol, with scanning beginning at the iliac crests superiorly and extending inferiorly to beyond the perineum. Image thickness will be 3mm, with images acquired every 2mm, thus providing sufficient image overlap to minimize the effects of patient motion on image quality and to provide for the creation of a high-resolution DRR.

Patients will be encouraged to fill their bladder by drinking 8-16 ounces of fluid prior to CT scan, but no specific bladder filling guidelines will be mandated.

6.2.5. Daily treatment localization will be achieved by acquiring orthogonal radiographs immediately prior to each daily treatment. To ensure adequate coverage of the prostate gland, wherein daily position can be influenced by varying amounts of bladder and rectal filling, the daily patient alignment will be performed with reference to bony landmarks. Alignment via reference to bone landmarks will remain our primary alignment technique. All positioning images and table shifts are to be reviewed by a physician prior to each day's treatment.

6.3 Treatment Planning/Target Volumes

6.3.1. The GTV is defined by the physician as all known disease as defined by the planning CT scan, additional imaging studies (ultrasound, MRI) and clinical information. The GTV for the purposes of this protocol is the prostate gland only.

6.3.2. The CTV is the GTV plus areas considered to be at risk for containing microscopic tumor. The CTV for the purposes of this protocol is the GTV.

6.3.3. The PTV (Planning Target Volume) will provide a margin around the CTV to compensate for patient motion, variations in daily set-up position, and beam physics. For the purposes of this protocol, the PTV will be defined as the CTV + 12 mm in all directions.

6.3.4. Treatment will be administered to the PTV via multiple conformal proton beams, with all fields being treated daily. It is anticipated that for most if not all patients a lateral beam arrangement will be employed, although other beam configurations may be permitted subject to the normal tissue constraints listed in section 6.3.6. and the approval of the principal investigator.

6.3.5. Critical Normal Structures

6.3.5.1. DVH data will be generated for the following normal tissues:

Bladder-with organ contoured from dome to neck.

Rectum-Contoured from the recto-sigmoid junction to the inferior border of the ischial tuberosities. The entire outer circumference should be contoured.

Femoral heads-Contoured from the acetabular roof to the inferior edge of the greater trochanter.

6.3.6. Normal Tissue Constraints (adapted from arm II of the RTOG 0415 Study, assumes an α/β of rectum and bladder=3).

	No more than 15% volume exceeds	No more than 25% volume exceeds	No more than 35% volume exceeds	No more than 50% volume exceeds
Bladder	60 CGE	55 CGE	51 CGE	48 CGE
Rectum	60 CGE	55 CGE	50 CGE	45 CGE

6.3.7. The prescription dose is to the isocenter of the PTV. The maximum dose to the PTV should not exceed the Rx dose by $>5\%$, and the minimum dose to the PTV should not be $<90\%$ of the Rx dose.

The Rx is 3 CGE/Day to isocenter, one treatment per day, 5 days per week, for 20 treatments (=60 CGE to isocenter/20 fractions).

6.4 Radiation Toxicity

6.4.1. All patients will be seen and examined weekly by their attending radiation oncologist during treatment. Any and all observations regarding radiation reactions will be recorded and should include particular attention to the following side effects:

6.4.1.1. Small bowel or rectal irritation manifesting as abdominal cramping, diarrhea, rectal urgency, proctitis, or hematochezia.

6.4.1.2. Bladder complications including urinary frequency/urgency/dysuria, hematuria, urinary tract infection, incontinence, nocturia.

6.4.1.3. Radiation dermatitis.

6.4.1.4. Clinical discretion may be exercised to treat radiation-induced side effects with the appropriate OTC and/or prescription medications.

7.0 Drug Therapy-N/A

8.0 Surgery-N/A

9.0 Other Therapy

9.1. Neoadjuvant or Adjuvant Hormonal Therapy.

Neoadjuvant or adjuvant hormonal therapy is not allowed in this trial. The patient population for this trial was chosen to include only those patients who did not stand to benefit from the use of hormonal therapy (by virtue of their favorable disease status). As a secondary goal of this trial is to determine the effect of hypofractionated conformal proton beam radiation therapy on bNED survival, hormonal therapy would simply confound the impact of hypofractionated radiation on bNED survival and freedom from relapse.

9.2 Subsequent disease progression.

Patients who have failed as defined by criteria described in Sections 11.4 (criteria for biochemical recurrence), 11.5 (criteria for local recurrence), or 11.6 (criteria for non-local recurrence) may receive additional medical and/or surgical therapy as appropriate for the clinical situation. These would include salvage prostatectomy, salvage cryosurgery, androgen-ablation therapy, cytotoxic chemotherapy, observation, or participation in an appropriate clinical trial.

11.0 Patient Assessments

11.1 Study parameters

Assessments	Pre-Entry	Weekly During RT	Follow-Up (months)							
			3	6	9	12	15	18	21	24
History, physical exam	X	X	X	X	X	X	X	X	X	X ^c
Prostate biopsy with Gleason Score	X									X ^d
PSA	X ^a		X	X	X	X	X	X	X	X ^c
Digital Rectal Exam	X		X	X	X	X	X	X	X	X ^c
MRI/MRS	X ^b									
Baseline urinary status evaluation	X									
Toxicity evaluation		X	X	X	X	X	X	X	X	X ^c
Bone scan										X ^e

- a. PSA < 10 ng/ml within 180 days of registration
- b. Per Section 4.1.3
- c. Follow-up will continue every 6 months for the next 3 years, then annually thereafter
- d. Per Section 11.3.4
- e. Per Section 11.3.3

11.2. Evaluation During Treatment

11.2.1. Patients will be seen and evaluated at least weekly during treatment with documentation of treatment tolerance and the presence/absence/magnitude of acute reactions.

11.3 Evaluation Following Treatment

11.3.1. At each visit the patient will have an interval history, disease-focused physical examination (including DRE) and assessment of any specific GI/GU toxicity.

11.3.2. PSA will be drawn at each follow up visit: 3 months post radiation therapy, then every three months for two years, then every six months for three years, then annually.

11.3.3. A Bone scan will be performed as clinically indicated e.g., if the patient develops a PSA recurrence with a rapid doubling time (< 6 months) or if the patient develops symptoms suggestive of metastatic disease.

11.3.4. A needle biopsy is encouraged from the site of original tumor within the prostate and/or other sites or within the gland as identified by TRUS and/or MRI for rising PSA or clinical failures (see Sections 11.5.1. and 11.6.1).

11.4 Criteria for Biochemical Recurrence

11.4.1. Biochemical (PSA) recurrence will be defined as per the new RTOG/ASTRO criteria known as the RTOG Phoenix definition: an increase of the PSA level of at least 2 ng/ml greater than the post-treatment nadir. To ensure valid comparisons with our institutional data, the ASTRO Consensus Conference definition (three successive > 10% rises in PSA above a nadir) will also be used, although this definition will not be the primary definition of biochemical failure.

11.5 Criteria for Local Recurrence

11.5.1. Clinical criteria for local recurrence are progression (increase in size of a palpable abnormality) at any time, failure of regression of the palpable tumor by two years post-treatment, and redevelopment of a palpable abnormality after complete disappearance of the previously appreciated abnormality. The presence of palpable disease must be recorded on the data collection forms for initial and follow up patient evaluations.

11.5.2 Histologic criteria for local recurrence are presence of prostate carcinoma upon biopsy and positive biopsy of the palpably normal prostate > 2 years from the end of treatment.

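### The clinical local-recurrence criteria in Section 11.5.1 omit a first palpable abnormality in a gland that was impalpable at baseline, so local progression in T1 patients can go uncounted or be dated late

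*Combined protocol and SAP*

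**What the plan says.** Section 2.2.1 makes local progression a secondary outcome, to be no worse than the institutional standard, and quotes a percentage for reference: "local progression (5-year rate in PROG was 7" (per cent). It does not say how that source defined local progression.

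Section 3.1.4 sets the stage range: "Clinical stage T1-T2C as per the AJCC, 6th edition".

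Section 11.5.1 gives the clinical criteria for local recurrence. The first two are "progression (increase in size of a palpable abnormality) at any time, failure of regression of the palpable tumor by two years post-treatment". The third is "redevelopment of a palpable abnormality after complete disappearance of the previously appreciated abnormality". The same section requires palpable disease to be recorded on the forms at baseline and at follow-up.

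Section 11.5.2 is a separate, histologic route: "Histologic criteria for local recurrence are presence of prostate carcinoma upon biopsy and positive biopsy of the palpably normal prostate > 2 years" after the end of treatment.

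Section 11.3.4 encourages, but does not require, a needle biopsy "for rising PSA or clinical failures (see Sections 11.5.1. and 11.6.1"). Sections 11.1 and 11.3.1 schedule a DRE at every follow-up visit.

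**The concern.** T1 is taken here in its usual sense of a tumor that cannot be felt on DRE. In such a patient, a nodule felt for the first time during follow-up is a natural clinical sign of possible local failure, but no criterion in 11.5.1 names it. Whether a new DRE finding counts then depends on the patient's stage at entry, and the protocol gives no reason for the difference.

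The fallback is partly circular. The biopsy that could bring the nodule in under 11.5.2 is prompted by a rising PSA or by a clinical failure, and clinical failure is defined by reference to the list that leaves the nodule out.

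At stake is the local progression rate to be set beside 7%. Leaving out a route to the event can only lower or delay the count relative to a definition that includes it. An investigator might also read first appearance as an increase in size, in which case coding would vary between assessors.

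**Working it through.** **1. The plan's own figure.** The 7% is a cited historical rate with no inputs in the protocol, so it cannot be reproduced. The point turns on reading the definitions.

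**2. The criteria applied to a new nodule in a T1 patient, at the DRE that first finds it.**

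| Criterion | What it needs | Met at first appearance? |
|---|---|---|
| 11.5.1, first: "progression (increase in size of a palpable abnormality) at any time" | A palpable abnormality that has grown; palpability at baseline is not required | No; yes if it is larger at a later visit |
| 11.5.1, second: "failure of regression of the palpable tumor by two years post-treatment" | A palpable tumor that should have regressed | No |
| 11.5.1, third (redevelopment) | An earlier palpable abnormality that disappeared completely | No |
| 11.5.2 (histologic) | Carcinoma on biopsy; no earlier palpability needed | Only if biopsied and positive |

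A T2 patient whose lesion had disappeared, and who has the same new finding at the same visit, meets the third criterion at once.

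**3. Delay when the growth route applies.** Section 11.1 schedules visits every 3 months to month 24, every 6 months for the next 3 years (to 24 + 36 = 60 months), then annually. A nodule that counts only once it has grown is dated at least one visit late: 3, 6 or 12 months on the schedule. One first felt at month 60 and larger at the next annual visit, month 72, falls outside a 5-year rate.

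**4. Illustration of size.** Let s be the share of local failures that occur in T1 patients, and m the share of those never captured by 5 years. As a crude proportion:

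observed rate = 7% × (1 − s × m)

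The protocol gives neither s nor m. The values below are assumptions. Expected events among 187 patients are in brackets; the true count would be 187 × 0.07 = 13.1.

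| s | m = 0 | m = 10% | m = 25% | m = 50% |
|---|---|---|---|---|
| 40% | 7.0% (13.1) | 6.72% (12.6) | 6.3% (11.8) | 5.6% (10.5) |
| 60% | 7.0% (13.1) | 6.58% (12.3) | 5.95% (11.1) | 4.9% (9.2) |
| 80% | 7.0% (13.1) | 6.44% (12.0) | 5.6% (10.5) | 4.2% (7.9) |

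The most extreme cell is 7% × (1 − 0.8 × 0.5) = 4.2%. The left column, with no loss, applies if every such nodule is biopsied or is counted on growth within five years.

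**5. Effect on planned decisions.** The planned sizes do not use local recurrence. A search for the smallest exact one-sample binomial design with both error rates at most 10% returns 187 patients for 5% against 10% biochemical failure (actual error rates 0.087 and 0.098) and 105 for 1% against 5% toxicity (0.089 and 0.099). Both match Section 12.2.1. The go/no-go rule in 12.2.1.3 uses late toxicity and biochemical failure. Local progression has no margin, test or cut-off and is not listed in Section 12.1.

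**The case against.** The strongest reply is that the gap is narrow and its effect unproven. Most of this stands.

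- **Other routes exist.** A reader might infer that a new nodule in a T1 patient can never be a local recurrence, or that T1 patients cannot reach the clinical endpoint. The text does not support that. A positive biopsy counts whatever the baseline palpability, and growth counts at any time.
- **The bias against 7% is not demonstrated.** The benchmark's definition is not given. If it used the same criteria, the rule would be the same on both sides, although any loss would still scale with the T1 share. Section 2.2.1 quotes benchmark results for intermediate/high-risk as well as low-risk patients, while this trial takes low-risk patients only, so an equal stage mix cannot be assumed.
- **Other wording could raise the count.** The first histologic criterion states no minimum time after treatment.
- **The data are not lost.** DRE findings are recorded at each visit, a rising PSA prompts the encouraged biopsy by itself, and nothing forbids a biopsy in other circumstances.
- **A wider definition has consequences.** Section 9.2 refers to 11.5 when it says who may receive further treatment, and 11.3.4 refers to it for biopsy. Any change must therefore be confined to the analysis unless the sponsor reconciles those sections.

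What remains is that a nodule neither biopsied positive nor seen to grow is uncounted, and one that grows is counted late. Recording a finding does not classify it.

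**Conclusion.** The gap in 11.5.1 is real and follows from the text alone: first appearance of a palpable abnormality in a previously impalpable gland is not a clinical local recurrence, although T1 patients are eligible. The 5-year local progression rate can be biased downward by an amount the protocol does not allow to be estimated. The span of 7.0% to 4.2% rests entirely on assumed values of s (40% to 80%) and m (0 to 50%).

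A reader might go further and multiply 7% by one minus an assumed T1 share. Shares of 30% to 80% give 4.9% down to 1.4%, as if the new schedule could look 30% to 80% better than it is. That calculation sets m to 100% and assumes the same 7% rate in both stages. It ignores both the biopsy and the growth routes, so the documents do not support it as an estimate.

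The consequence is limited to a named secondary outcome. It merits correction because the comparison is stated as an objective and the remedy uses data already collected.

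**What to change.** For the local progression analysis, add a fourth criterion to 11.5.1: a new palpable prostate abnormality not present at baseline (including in T1 patients), dated at the first DRE that records it, and not counted if biopsy of it is negative. Report the 5-year rate with and without this criterion, and state the benchmark's definition of local progression beside the 7%, so that the reader can see which version is comparable.

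The sponsor should reconcile 11.3.4 and 9.2 with the revised definition, saying whether the added criterion serves the analysis only. No biopsy or salvage rule is proposed here.

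The cost is one clause, a form item that separates a new abnormality from a known one, and a second line in the results. The analysis itself needs no added visit or procedure. The price is a slightly less favorable rate, and some benign nodules counted where no biopsy is done; the paired report shows how much the criterion contributes.

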11.6 Criteria for non-local recurrence

11.6.1. Distant metastasis will be documented if clinical, bone scan, or other imaging studies (Prostascint, MRI) demonstrates evidence of its existence. Whenever possible, distant metastasis should be documented by histologic confirmation. In addition, TRUS/ biopsy of the prostate is recommended at the time distant metastasis are reported.

11.6.2. Regional metastasis will be documented if there is imaging evidence of lymphadenopathy and histologic confirmation.

12.0 Statistical Considerations

12.1 Study Endpoints

12.1.1. Rate of late GI and GU toxicities \geq grade 3 (see Appendix for scoring scheme)

12.1.2. Three-year actuarial rate of freedom from biochemical failure.

12.2. Sample Size

12.2.1. Sample Size

12.2.1.1. Phase I Component: Between 1990 and 2007, we have treated 4260 patients with early stage prostate cancer (clinical stage T1 or T2, initial PSA <10 ng/ml, KPS 90 or 100) with protons only. The 3-year actuarial rectal/urinary grade 3 toxicity rate was $0.69\% \pm 0.15\%$ SE in this cohort. We will conservatively assume the standard toxicity rate p_0 to be 1% and set the unacceptable toxicity rate p_1 at 5%. Statistical error rates will be set at $\alpha=10\%$ for a false positive result (calling the treatment too toxic when it is not) and $\beta=10\%$ for a false negative result (accepting that the treatment is not too toxic when in reality it is) when using a one-sided test of significance. The sample size meeting these requirements is 105 patients.

12.2.1.2. Phase II Component: In the same patient cohort, the 3-year actuarial rate of biochemical progression free survival (bPFS) was 96%. We will conservatively assume the standard 3-year biochemical failure rate p_0 to be 5% and set the unacceptable failure rate p_1 at 10%. Statistical error rates for false positive and false negative results will again be set at 10%. The required sample size is 187 patients, which exceeds the required sample size for the toxicity endpoint. An additional 35% will be added to this number to guard against ineligible or evaluable cases, resulting in 288 patients. In order to be conservative the sample size for the Phase I/II study will be set to 300 patients.

12.2.1.3. Assuming we accrue the target goal of 187 evaluable patients, a 5% late toxicity rate equates to 9.34 patients with toxicity. If we have 9 or fewer patients with toxicity, the protocol therapy will be considered for further study. In addition, we must also meet the goals for tumor control. Assuming the target goal of 187 patients, tumor control will be considered acceptable if 12 or fewer patients have biochemical failure within the first three years. For the protocol therapy to be recommended for further study, both the toxicity and tumor control outcomes must be considered acceptable. This equates to 9 or fewer patients with late toxicity, and 12 or fewer patients with recurrence. If the study accrues more or less than 187 evaluable patients, these cut-off numbers will be adjusted accordingly.

With a sample size of 187 patients and an assumed late toxicity rate of 2%, we have an upper = 95% confidence limit of 5% for (grade ≥ 3) late toxicity. This upper bound corresponds to the limit we would accept in terms of toxicity.

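### The tumour-control benchmark comes from a historical cohort that is not shown to match the trial's Gleason 2-6, hormone-free population or its 81 CGE/45-fraction comparator.

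*Combined protocol and SAP*

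**What the plan says.** The benchmark cohort is described in section 12.2.1.1 as 4260 "patients with early stage prostate cancer (clinical stage T1 or T2, initial PSA <10 ng/ml, KPS 90 or 100) with protons only", treated between 1990 and 2007. Section 12.2.1.2 then states: "In the same patient cohort, the 3-year actuarial rate of biochemical progression free survival (bPFS) was 96"%. From that figure it proceeds: "We will conservatively assume the standard 3-year biochemical failure rate p_0 to be 5% and set the unacceptable failure rate p_1 at 10"%. Section 12.2.1.3 turns this into a rule: with 187 evaluable patients, tumour control is acceptable if at most 12 fail biochemically within three years. Passing this rule and the late-toxicity rule is required for a recommendation for further study.

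Eligibility is narrower. Section 3.1.4 requires "Clinical stage T1-T2C as per the AJCC, 6th edition, and Gleason Score 2-6, and PSA < 10 ng/ml". Sections 3.2.6 and 9.1 rule out hormonal therapy before and with the trial treatment. The institutional standard is identified as 81 CGE in 45 fractions (sections 1.3, 1.8 and 2.1), and section 2.2.1 asks whether biochemical control is no worse than with that standard.

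Section 2.2.1 also gives the only rates by risk group: "3-Year Actuarial rate in PROG was 96% for low risk patients, 90% for intermediate/high risk patients".

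**The concern.** There is no concurrent control, so the cohort rate is the comparator. Its description goes as far as performance status but gives no Gleason, hormonal-therapy or dose/fractionation criterion. The reader therefore cannot tell whether 96% is the rate for men like those in the trial, treated with the stated standard.

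The Gleason gap has a predictable direction. The PROG figures show lower control in higher-risk men. If such men are in the cohort, its 4% failure rate is higher than the rate for Gleason 2-6 men on the same treatment, and the trial's better-prognosis men face an easier bar. Part of an apparent finding of no worse control could then come from case selection.

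Rounding adds to this. Moving p0 from the observed 4% up to 5% is called conservative, but for a no-worse-than claim a higher p0 is lenient. At stake is one of the two conditions for recommending the regimen for further study.

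**Working it through.** **Inputs (section 12.2.1 unless noted).** Cohort failure 4% (100% − 96%); p0 = 5%; p1 = 10%; error rates "Statistical error rates for false positive and false negative results will again be set at 10"%; one-sided testing, stated for the toxicity component ("when using a one-sided test of significance") and assumed to carry over; rule of at most 12 failures in 187. From section 2.2.1: PROG three-year failure 4% in low-risk and 10% in intermediate/high-risk men.

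**1. Reproducing the plan.** The plan says: "The required sample size is 187 patients, which exceeds the required sample size for the toxicity endpoint". I searched for the smallest n with a cut-off c such that P(X > c | n, p0) ≤ 0.10 and P(X ≤ c | n, p1) ≤ 0.10, with X binomial.
- 5% against 10%: n = 187, c = 13. The errors are 8.7% (rejecting at p0) and 9.8% (passing at p1).
- 1% against 5%: n = 105, c = 2, which matches the plan's toxicity figure.

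The plan's cut-off of 12 is one stricter than this: it rejects at p0 with probability 14.6% and passes at p1 with 5.9%.

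**2. The stated rule.** P(X ≤ 12 | 187, p) by true failure rate p:

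| p | 2% | 3% | 4% | 5% | 6% | 8% | 10% |
|---|---|---|---|---|---|---|---|
| Pass | 0.9999 | 0.996 | 0.961 | 0.854 | 0.667 | 0.261 | 0.059 |

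These values depend only on the cut-off and n. They would be the same for any Gleason mix in the cohort.

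**3. What a mixed cohort would imply.** The documents do not give the mix, so this is an assumption with a range. Suppose a share f of the cohort had higher Gleason scores and failed at 10% (the PROG intermediate/high-risk figure, borrowed). Low-risk failure is then (0.04 − 0.10f)/(1 − f):
- f = 0: 4.0%
- f = 0.1: 0.030/0.9 = 3.3%
- f = 0.2: 0.020/0.8 = 2.5%
- f = 0.3: 0.010/0.7 = 1.4%

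**4. Cut-offs at the planned 187 for a matched p0.** For each p0, c is the smallest cut-off with P(X > c | 187, p0) ≤ 0.10.

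| p0 | Cut-off | Reject at p0 | Pass at 5% true failure | Pass at p0 + 5 points | Pass at 2 × p0 |
|---|---|---|---|---|---|
| 4% | ≤11 | 0.074 | 0.77 | 0.08 | 0.18 |
| 3% | ≤9 | 0.057 | 0.54 | 0.06 | 0.31 |
| 2.5% | ≤7 | 0.099 | 0.28 | 0.03 | 0.28 |
| 2% | ≤6 | 0.083 | 0.17 | 0.02 | 0.38 |
| Stated rule (p0 5%) | ≤12 | 0.146 | 0.85 | 0.06 | 0.06 |

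At 187 patients, a margin of 5 points keeps the chance of passing at p1 below 10% in every row. A p1 of twice p0, which is the plan's present ratio, does not do so in the four reset rows.

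**The case against.** A one-line description that omits Gleason score is not a statement that Gleason 7 or higher men were included. A reader might infer that the cohort had no Gleason limit and that the rule therefore passes regimens worse than the low-risk standard. The documents do not support that: they are silent on the mix. Likewise, the words protons only may have been meant to exclude hormonal therapy; the text does not say.

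The only low-risk figure in the documents, 96% from PROG, equals the cohort figure. Putting both PROG rates into the mixture in step 3 gives a higher-risk share of zero. This is real evidence that the shift may be small. It does not settle the point, because PROG is a different study and neither the arm nor the failure definition behind its rate is given.

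A reader might also attribute the 0.85 pass probability at 5% failure to case mix. It follows from p0 = 5% and the cut-off of 12, and would be the same with a perfectly matched cohort. The plan's cut-off is in fact stricter than the exact 13.

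Finally, this is a single-arm phase I/II study, biochemical control is a secondary objective, and passing leads only to further study. That limits the consequences but does not remove the need for a matched comparator. Nothing in the documents links Gleason score to late toxicity, so the Gleason argument does not extend to the toxicity benchmark.

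**Conclusion.** The concern holds as a matter of an unmatched benchmark, not of demonstrated bias. The stated cohort criteria do not cover Gleason score, hormonal therapy or the 81 CGE/45-fraction schedule, all of which define the trial population or its comparator. If higher-Gleason men are in the cohort, the bar is too low for the trial's men. How much too low cannot be determined from the documents.

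The range runs from almost nothing to material. If the matched rate is 96%, p0 is 4% and the cut-off moves from 12 to 11. If matched failure were 2.5%, which needs a 20% higher-Gleason share failing at 10%, the cut-off would be 7 and a regimen with 5% true failure would pass with probability 0.28 instead of 0.85. These figures assume one-sided 10% error, full three-year evaluability of 187 men, and the illustrative failure rates named above. Only the institution's own data can say where in this range the truth lies.

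**What to change.** Before the rule is fixed, recompute the cohort's three-year biochemical control in men with Gleason 2-6 and no hormonal therapy and, where numbers allow, treated with 81 CGE/45 fractions. Report it in section 12.2.1 with its standard error, the number of men, and the section 11.4 failure definition used.

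Use that rate as p0 without rounding it upward. Then restate p1 with its justification and reset the cut-off in section 12.2.1.3 at the planned 187, using the table under the working as a guide. If the subset rate is about 96%, the only change is p0 = 4% with a cut-off of 11 or fewer.

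The cost is a re-analysis of existing institutional data, as far as these items were recorded, and an edit to section 12.2. The sample size need not rise if the 5-point margin is kept. The downsides are a smaller benchmark cohort with a wider standard error and a stricter cut-off.

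### The late-toxicity cut-off of 9 or fewer in 187 accepts a true 5% rate 54% of the time, against the 10% beta set in section 12.2.1.1

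*Combined protocol and SAP*

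**What the plan says.** Section 12.2.1.1 designs the late-toxicity test: "We will conservatively assume the standard toxicity rate p_0 to be 1% and set the unacceptable toxicity rate p_1 at 5"%. The test is one-sided, with 10% for each error. The second error is described as being "for a false negative result (accepting that the treatment is not too toxic when in reality it is". The result is: "The sample size meeting these requirements is 105 patients".

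Section 12.2.1.2 needs 187 patients for biochemical failure and notes that this is more than toxicity requires. Section 12.2.1.3 sets the decision rule at 187. It observes that "a 5% late toxicity rate equates to 9.34 patients with toxicity" and continues: "If we have 9 or fewer patients with toxicity, the protocol therapy will be considered for further study". For the other endpoint, "tumor control will be considered acceptable if 12 or fewer patients have biochemical failure within the first three years". For a recommendation, "both the toxicity and tumor control outcomes must be considered acceptable". If the evaluable number differs from 187, "these cut-off numbers will be adjusted accordingly".

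The closing paragraph of section 12.2 assumes 2% late toxicity in 187 patients, quotes an upper 95% confidence limit of 5%, and calls this the limit that would be accepted.

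**The concern.** A cut-off placed at the count expected under the unacceptable rate splits that distribution near its middle. About half of all trials of a regimen at exactly that rate will fall at or below it, whatever the sample size. Such a rule cannot hold a 10% false-acceptance rate. Going from 105 to 187 patients should have reduced both errors; this rule raises the false-acceptance error more than fivefold.

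Late grade 3 or higher morbidity is the primary objective (section 2.1) and the first endpoint (section 12.1.1), so this is the toxicity half of the go/no-go decision. Section 12.2.1.1 gives a historical 3-year grade 3 rate of 0.69%. A 5% rate would be about seven times that (5 / 0.69 = 7.2), and the rule would pass it more often than not. The stopping rule in section 12.3 covers acute effects only.

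**Working it through.** **Inputs.** From 12.2.1.1: p0 = 1%, p1 = 5%, one-sided alpha = beta = 10%, n = 105. From 12.2.1.2: p0 = 5%, p1 = 10%, the same error rates, n = 187. From 12.2.1.3: accept at 9 or fewer toxicities and 12 or fewer biochemical failures of 187. Assumption: each endpoint is a simple proportion with complete follow-up.

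**Formulas.** With X binomial(n, p) and acceptance when X ≤ c: alpha = P(X > c | n, p0) and beta = P(X ≤ c | n, p1).

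**Reproducing the plan's sample sizes.** The smallest n with both errors at most 10% is:
- toxicity, 1% versus 5%: n = 105, c = 2, alpha 8.9%, beta 9.9%;
- biochemical failure, 5% versus 10%: n = 187, c = 13, alpha 8.7%, beta 9.8%.

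Both match, so exact binomial is evidently the plan's method.

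**The stated toxicity rule.** The expected count at p1 is 187 × 0.05 = 9.35 (printed as 9.34, which is immaterial). P(X ≤ 9 | 187, 5%) = 54.0%, so power is 46.0%. The probability of acceptance at other true rates is:

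| True rate | 1% | 2% | 3% | 4% | 5% | 6% | 7% |
|---|---|---|---|---|---|---|---|
| 9 or fewer of 187 | >99.99% | 99.5% | 94.3% | 78.2% | 54.0% | 31.0% | 15.0% |

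Acceptance falls to 10% only at a true rate of 7.5%.

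**Alternative toxicity cut-offs at n = 187.**

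| Accept if at most | Alpha at 1% | Beta at 5% |
|---|---|---|
| 3 | 11.9% | 1.5% |
| 4 | 4.1% | 4.1% |
| 5 | 1.2% | 9.0% |
| 6 | 0.3% | 17.0% |
| 9 | 0.002% | 54.0% |

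Only 4 and 5 keep both errors within 10%.

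**Effect of the joint rule.** At a 5% biochemical failure rate, P(X ≤ 12 | 187, 5%) = 85.4%. With toxicity also at 5%, the chance of a recommendation is 0.540 × 0.854 = 46% if the endpoints are independent. Under any dependence it lies between 0.540 + 0.854 − 1 = 39% and 54%.

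**Effect of adjusting for n.** The plan gives no method. If 9 is scaled in proportion to n, beta at 5% stays between about 41% and 62% for n = 150 to 300, depending on rounding. A cut-off of 9 first brings beta to 10% or less at n = 282 evaluable.

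**Confidence limit in section 12.2.** Exact upper 95% limits, one-sided / two-sided, are 4.8% / 5.4% for 4 of 187, 5.5% / 6.1% for 5 of 187 and 8.2% / 8.9% for 9 of 187. An accepted regimen with 9 events would be well over the 5% limit.

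**The case against.** - **The 10% beta is stated for the 105-patient calculation, not for the cut-off at 187.** Section 12.2.1.3 gives no error rates and can be read as a rule that the observed proportion should not exceed 5%. It is true that carrying the error rates over is an inference. It is a sound one: the plan gives no other late-toxicity error rates, 12.2.1.3 reuses the same 5%, and 12.2.1.2 presents 187 as more than toxicity requires.
- **The biochemical cut-off does not show that 12.2.1.3 was built to the stated errors.** This stands. Twelve or fewer meets its beta (5.9% at a 10% failure rate) but not its alpha (14.6% at 5%); 13 would meet both. The point about toxicity does not depend on it.
- **The tighter cut-offs have their own difficulties.** This also stands. Five of 187 exceeds the 5% upper limit in section 12.2 on either reading, and 4 of 187 meets it only one-sided. If the 2% assumed there were the benchmark, no cut-off at 187 would meet 10% for both errors against 5%: 5 gives alpha 17.4% and beta 9.0%, and 6 gives 8.3% and 17.0%.
- **The stakes are limited.** Passing leads only to further study, and section 1.4 reports no grade 3 or higher complications in 62 patients at this institution given 60 Gy in 20 fractions. At a true 5%, that has probability 0.95^62 = 4.2%. But minimum follow-up there was one year, so this lowers the concern about late effects without removing it, and it does not change what the rule does at 5%.

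**Conclusion.** The concern holds and must be fixed. The toxicity rule in 12.2.1.3 accepts a true 5% rate 54.0% of the time, where 12.2.1.1 allows 10%. No other part of the plan repairs this: the tumor-control condition leaves the chance of a recommendation at about 46% when biochemical failure is at its acceptable 5%, and the adjustment clause is undefined. The result rests on carrying the 12.2.1.1 error rates to 187 patients and on treating late toxicity as a complete binary outcome.

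**What to change.** 1. In 12.2.1.3, replace the toxicity cut-off of 9, in both places, with either 5 or fewer (alpha 1.2%, beta 9.0%) or 4 or fewer (alpha 4.1%, beta 4.1%). If 9 is kept, state that beta at 5% is 54%.
2. Define the adjustment for toxicity as the largest c with P(X ≤ c | n, 5%) ≤ 10% and P(X > c | n, 1%) ≤ 10%. This gives c = 2 at n = 105–110, 3 at 132–157, 4 at 158–183, 5 at 184–208, 6 at 209–233, 7 at 234–257, 8 at 258–281 and 9 at 282–300. No c qualifies below 105 or at 111–131; report the attained errors there. If 4 of 187 is chosen, use the same rule with the first limit at 5%. That gives 4 at n = 181–207 and no qualifying c at 176–180 or at 152 and below.
3. Reconcile the chosen cut-off with the upper 95% limit at the end of section 12.2, and state whether that limit is one- or two-sided.
4. Confirm that 1% is the intended benchmark. Section 12.2 also assumes 2%, and section 2.1 quotes PROG 9509 grade 3 or higher rates of 1% (GI) and 3% (GU), which combine to roughly 3–4% depending on overlap (an assumption). At 2%, 3% or 4% no cut-off at 187 meets both 10% errors against 5%. The most balanced are 7 or fewer at 3% (alpha 20%, beta 28%) and 8 or fewer at 4% (alpha 33%, beta 41%). In any of these cases p0, p1 or the error rates would have to be restated.

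**Cost.** With p0 = 1% this is a change of wording and needs no extra patients. The price is more frequent rejection of regimens with intermediate true rates:

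| True rate | 1% | 2% | 3% | 4% |
|---|---|---|---|---|
| Rejected, 9 or fewer | 0.002% | 0.5% | 5.7% | 22% |
| Rejected, 5 or fewer | 1.2% | 17% | 49% | 76% |
| Rejected, 4 or fewer | 4.1% | 32% | 66% | 87% |

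A regimen that only matched the PROG 9509 rates would therefore fail about half the time or more under either replacement.
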